6.2.5. Subgroup Analyses of Primary Efficacy Endpoint

Subgroup analyses will be performed to evaluate the consistency of the primary analysis results across subgroups defined by demographic and baseline characteristics. Analyses will be performed for the primary efficacy endpoint (change from baseline in total area of GA lesion(s) in the study eye at Month 12) for each of the following subgroups (as appropriate per actual subgroup sample size, levels with low sample size may be pooled to allow for an analysis to be conducted):

- Age Group (<75 years, 75 to <85 years, ≥85 years)
- Sex (male, female)
- Race (White, Black or African American, Asian, American Indian or Alaskan Native, Native Hawaiian or other Pacific Islander, multiple, unknown)
 - Note: If most subjects (e.g., >90%) are of a single race, this analysis will not be conducted.
- Geographic Region (United States vs Rest of World)
- Subgroups indicative of disease severity at baseline
 - Study eye baseline GA lesion size (<7.5 mm²; ≥7.5 mm²)
 - Study eye baseline GA lesion size categories (approximately tertiles based on APL2-303/304 combined data*)
 - Study eye baseline NL-BCVA categories (≥70, ≥60 - <70, ≥35 - <60, <35 ETDRS letters)
 - Study eye baseline NL-BCVA categories (<60 vs. ≥60 ETDRS letters)
 - Study eye baseline LL-BCVA categories (approximately tertiles based on APL2-303/304 combined data*)
 - Study eye baseline monocular maximum reading speed categories (approximately tertiles based on APL2-303/304 combined data*)
 - Baseline FRI Level (1,2,3,4)

- Subgroups associated with GA progression
 - Study eye baseline GA focality (multifocal, unifocal)
 - Study eye baseline GA lesion location (subfoveal involvement, without subfoveal involvement)
 - Baseline GA laterality (bilateral GA (with or without CNV in fellow eye) vs. Study eye GA Only)
 - Baseline CNV in fellow eye (Fellow eye CNV vs. No fellow eye CNV)
 - Study eye baseline LLD categories (<20 vs. \geq 20 ETDRS letters)
 - Study eye baseline LLD categories (approximately tertiles based on the APL2-303/304 combined data*)
 - Study eye baseline NL-BCVA (<60 vs. \geq 60 ETDRS letters) and LLD (<20 vs. \geq 20 ETDRS letters) combinations

*Approximately tertiles will be specified consistently across the APL2-303/304 studies to the nearest clinically relevant level.

For the primary efficacy endpoint, the approach described in the Section 6.2.2 will be used for each subgroup analysis based on the data subset for the subject subgroup of interest. Baseline covariates included in the main analysis but no longer relevant given the subgroup of interest will be excluded from the model. The estimated treatment effects (PM vs. Sham; PEOM vs. Sham) and corresponding 95% CIs and p-values from the models will be displayed graphically for each pegcetacoplan treatment arm and each level of the subgroups specified (e.g., via forest plots).

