6.2.2. Main Analysis of Primary Efficacy Endpoint

The primary endpoint will be analyzed in the mITT population with subjects grouped according to the treatment assigned at randomization.

A MMRM model will be used to analyze the primary endpoint. The analysis model will include treatment (PM, PEOM, sham), presence of choroidal neovascularization in the fellow eye at baseline (Yes, No) and baseline GA lesion area ($< 7.5 \text{ mm}^2$ or $\geq 7.5 \text{ mm}^2$) as fixed effects, time (study month, categorical) as a factor, the time \times treatment interaction term, and the baseline GA lesion area ($< 7.5 \text{ mm}^2$ or $\geq 7.5 \text{ mm}^2$) \times time interaction term. The least square [LS] mean change from baseline to Month 12 will be estimated from the model for each of three arms as well as the comparisons of each of the three arms to each other. For other time points of interest, LS mean change from baseline will be estimated and compared between treatments. For each estimated LS mean, the corresponding 95% CI will be presented based on the model. For the comparison of the LS means, the corresponding 95% CI and the 2-sided P-value along with the percentage difference (difference in LS means between the arms/the comparison group LS mean) will be

presented. A common unstructured covariance matrix will be used to model the within-subject errors, the sandwich estimator (Diggle, Liang, and Zeger 1994) will be used to estimate the standard errors of the fixed effects parameters, and the degrees of freedom will be partitioned into between-subject and within-subject portions. If there are convergence problems with the model, then a heterogeneous autoregressive (1) covariance matrix will be used. If convergence problems still exist, an autoregressive (1) covariance matrix will be used. The LS mean of the change from baseline in the total area of GA lesion(s) \pm the standard error will be plotted over time by treatment group.

The observed values for the total area of GA lesion(s) will be summarized by treatment group and visit for both the study and the fellow eye. Summaries will present the descriptive statistics for baseline, absolute values and change from baseline data by visit.

The mean change from baseline in the total area of GA lesion (s) in the study eye \pm the standard error will be plotted over time by treatment group.

All GA lesion (s) size data will be listed for the ITT set.

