1.2.1 Mixed Effect Model for Repeated Measure

```
*-----  
* Read Analysis data  
*-----  
* In this example, repeated measures are available at  
* avisitn = 0.5 (baseline), 2 (Month 2),  
* 6 (Month 6), and 12 (Month 12)  
*-----;  
  
data ga;  
  set adam.adga;  
  if paramcd = 'SEGAORG' and  
  avisitn in (0.5, 2, 6, 12) and  
  ANL01FL = 'Y';  
  
  * trtan (actual treatment[number])  
  * 1 = APL-2 Monthly  
  * 2 = APL-2 Every Other Month  
  * 3 = pooled Sham group;  
  if trtan in (4,5) then trtan = 3;  
  
  * trt01 are trt02 are used in multiple imputation  
  * trt01 = 1 if Sham group  
  * trt02 = 1 if APL2 Monthly group  
  * trt01 = trt02 = 0 for APL2 EOM group;  
  if trtan = 3 then trt01= 1; else trt01 = 0;  
  if trtan = 1 then trt02= 1; else trt02 = 0;  
  
  * avisitc will be used in PROC TRANSPOSE;  
  if avisitn = 0.5 then avisitc = '00'; * Baseline;  
  if avisitn = 2 then avisitc = '02'; * Month 2;  
  if avisitn = 6 then avisitc = '06'; * Month 6;  
  if avisitn = 12 then avisitc= '12'; * Month 12;  
run;  
  
*****;  
*** MAIN ANALYSIS using MMRM ***;  
*****;  
  
proc mixed data=ga method=reml covtest empirical;  
  where avisitn NE 0.5; * exclude rows for baseline;  
  * cnv (CNV in the fellow eye)  
  * 0 = No  
  * 1 = Yes;  
  *base cat (baseline lesion size (<7.5 vs. ≥ 7.5));  
  class trtan cnv avisitn usubjid base_cat;  
  model chg = trtan cnv base_cat avisitn trtan*avisitn base_cat*avisitn  
  /cl;
```

```
repeated avisitn / subject=usubjid type=un r;  
lsmeans trtan*avisitn/pdiff cl e alpha=.05;  
ods output diffs= diff1 LSMeans= LSMean1;  
run;
```

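### Subgroup models keep the uncorrected sandwich standard error, so 95% intervals in levels of about 20 or fewer subjects per arm are somewhat too narrow

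*SAP*

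**What the plan says.** SAP 6.2.5 lists the subgroups for the primary endpoint and states that "the approach described in the Section 6.2.2 will be used for each subgroup analysis based on the data subset" for the level concerned. The model is therefore refitted in each level. Treatment effects, 95% CIs and p-values for both pegcetacoplan arms go into forest plots.

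The approach in SAP 6.2.2 is as follows: "A common unstructured covariance matrix will be used to model the within-subject errors, the sandwich estimator" supplies the standard errors, and "the degrees of freedom will be partitioned into between-subject and within-subject portions". The sample code in Appendix 1.2.1 matches: "proc mixed data=ga method=reml covtest empirical", with "repeated avisitn / subject=usubjid type=un r". Neither place names a small-sample correction.

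On small levels, 6.2.5 makes the analyses conditional, "as appropriate per actual subgroup sample size", and adds that "levels with low sample size may be pooled to allow for an analysis to be conducted". Race has its own rule: if most subjects (more than about 90%) are "of a single race, this analysis will not be conducted".

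Section 6.2.6 repeats the subgroup analyses for the 24-month data. Section 6.3.5 uses a similar model for the key secondary endpoints.

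**The concern.** The sandwich estimator builds the variance from squared residuals. With few subjects the fitted model absorbs part of the noise, so the residuals are too small and the variance is biased downward. At 200 per arm this does not matter. In a level with 10 or 15 per arm the intervals are too short and the p-values too small, and these are the levels where estimates are noisiest. The plots cover many levels, two active arms, two reporting times and several endpoints, so an apparent benefit or harm in a small level could look firmer than the data allow.

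**Working it through.** **1. The plan's own figure.** SAP 3.4 gives 200 per arm, SD 1.50 mm², mean growth of 1.47, 1.70 and 2.13 mm²/year, and two-sided alpha 0.0495. The differences from sham are 2.13 − 1.47 = 0.66 and 2.13 − 1.70 = 0.43. The noncentrality is difference / (1.50 × √(2/200)) = difference / 0.15, that is 4.40 and 2.87. With 597 df the critical t is 1.968, and power is 99.2% and 81.5%, as stated in Table 1 of the SAP. The documents state no subgroup size, interval width or coverage.

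**2. Hand approximation.** Take a level with N subjects, N/3 per arm. At each visit the 6.2.2 model fits about five coefficients: three arm means, lesion-size category and fellow-eye CNV. The uncorrected sandwich does not allow for them, so its SE is roughly √((N − 5)/N) of the correct one. Coverage is then about P(|t on N − 5 df| ≤ √((N − 5)/N) × t(0.975, df)).

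Section 6.2.2 does not say which df portion the Month 12 contrast receives, so both are shown:
- subject-based: N − 5;
- observation-based, with six FAF visits and 25 coefficients (18 + 6 + 1): 6N − N − (25 − 5) = 5N − 20.

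Example with 10 per arm, N = 30: √(25/30) = 0.913. Subject-based: 2.060 × 0.913 = 1.88, coverage 92.8%. Observation-based (130 df): 1.978 × 0.913 = 1.81, coverage 91.7%.

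**3. Simulation of the 6.2.2 model.** The setting has six visits (Months 2 to 12), treatment × month, lesion size × month, CNV, unstructured covariance, Month 12 SD 1.5 and complete data. Assumed, because the documents do not give them: level sizes, correlation pattern, CNV prevalence 25%, large lesions 50%. There were 3,000 to 6,000 replicates per row, with a Monte Carlo SE of about 0.3 to 0.5 points. A few replicates were lost at the smallest sizes. Coverage pairs are observation-based / subject-based df.

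| Per arm | Level N (share of 600) | SE ratio, formula | SE ratio, simulated | Coverage %, formula | Coverage %, simulated | Model-based SE, subject df, % |
|---|---|---|---|---|---|---|
| 5 | 15 (2.5%) | 0.816 | 0.859 | 86.7 / 90.1 | 86.1 / 89.7 | 96.1 |
| 8 | 24 (4%) | 0.890 | 0.897 | 90.6 / 92.2 | 90.6 / 91.9 | 95.4 |
| 10 | 30 (5%) | 0.913 | 0.920 | 91.7 / 92.8 | 91.3 / 92.5 | 95.3 |
| 15 | 45 (7.5%) | 0.943 | 0.944 | 93.0 / 93.6 | 92.7 / 93.3 | 95.2 |
| 20 | 60 (10%) | 0.957 | 0.956 | 93.5 / 94.0 | 93.3 / 93.8 | 95.2 |
| 30 | 90 (15%) | 0.972 | 0.979 | 94.1 / 94.3 | 94.1 / 94.3 | 95.1 |
| 50 | 150 (25%) | 0.983 | 1.015 | 94.4 / 94.6 | 94.9 / 95.1 | 95.6 |
| 67 | 201 (33.5%) | 0.987 | 1.009 | 94.6 / 94.7 | 95.2 / 95.3 | 95.5 |

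The simulated ratios above 1 in the last two rows reflect Monte Carlo error in the reference SD; the model-based SE shows the same excess there (1.033 and 1.021).

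Most of the shortfall comes from the sandwich. Moving from observation-based to subject-based df recovers 3.6 points at 5 per arm but only 1.2 at 10 and 0.5 at 20.

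**4. With drop-out and over 24 months.**
- Six visits, 15% drop-out, subject-based df (1,000 runs, Monte Carlo SE about 0.8): 93.3, 93.9, 93.5 and 94.1% at 10, 15, 20 and 30 per arm. Model-based: 95.8, 95.2, 95.1 and 94.9%.
- Twelve visits, 20% drop-out (450 runs, Monte Carlo SE about 1.2): 92.0, 92.4 and 94.2% at 10, 15 and 20 per arm. Model-based: 95.5, 94.7 and 96.2%.

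**The case against.** The other side has a good deal to say.

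- **No small level is shown to exist.** Coverage of 91 to 93% needs 10 to 15 per arm, that is 30 to 45 of 600 subjects in a level. The documents give no counts. Inclusion criterion 2 (24 letters or better) makes NL-BCVA below 35 a band of about 11 letters, but that limits the score range, not the number of subjects. This stands.
- **The plan already has safeguards.** Unsuitable levels need not be run, small ones may be pooled, and race may be dropped. This stands in part: the first two are discretionary, no minimum is stated, and the pooling clause aims at making an analysis possible rather than at valid intervals.
- **Multiplicity matters more.** Without race, 6.2.5 lists 45 levels, hence 90 comparisons and 90 × 0.05 = 4.5 expected chance findings if there were no effect. If four levels (8 tests) rejected at 8.2%, the rate in a six-visit simulation with 15% drop-out and observation-based df at 10 per arm, that adds 8 × 0.032 = 0.26. This stands and limits the importance of the point.
- **Comparability.** A different estimator in the subgroups means they are no longer computed exactly like the result they are checked against. True, but a modest price.
- **The remedy was checked through a stand-in.** The simulations used the model-based SE with subject-based df, not Kenward-Roger itself.

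A reader might also infer that the plots borrow standard errors or df from the 600-subject fit. They do not: the model is refitted on the subset, so both are re-estimated there, and only the method carries over. Nor do the documents establish that the df are counted on observations. Section 6.2.2 says only that they are partitioned, and the sample code for this model sets no df option.

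**Conclusion.** The point holds as a cheap improvement of limited reach. In levels with roughly 20 or fewer subjects per arm, the planned 95% intervals cover about 91 to 94%, and about 86 to 90% at 5 per arm. The loss is about 1 point at 30 per arm and negligible from 50.

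It would be wrong to read this as a fault in all the forest plots. An even tertile has about 67 per arm and an even two-level split about 100; neither is affected. An even four-way split of FRI or of the NL-BCVA-by-LLD cells gives 50 per arm, so only uneven levels are exposed. The candidates are NL-BCVA below 35, some FRI levels, some NL-BCVA-by-LLD cells and minority race groups. Whether any of them is small enough cannot be settled from the documents.

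The subgroups check consistency and carry no allocated alpha, and the primary analysis at about 200 per arm is unaffected. The figures rest on the assumed correlation pattern and covariate prevalences and on equal arms within a level. The main table also assumes complete data. The functional endpoints in 6.3.5 have other visits and covariates and were not simulated; the mechanism carries over, the exact figures may not.

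**What to change.** Add one sentence to SAP 6.2.5 and carry it into 6.2.6 and 6.3.5. Subgroup models use a small-sample-corrected analysis: either the model-based unstructured covariance with Kenward-Roger degrees of freedom, dropping the EMPIRICAL option, or a bias-corrected sandwich. Use the bias-corrected sandwich also where the autoregressive fallback of 6.2.2 is triggered, because the model-based SE then depends on a simpler matrix being right. Leave the primary model as written.

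Stating a minimum number per arm, below which a level is pooled or shown only descriptively, would make the existing pooling clause concrete and is a sensible addition.

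The cost is one code option and one sentence, slightly wider intervals in small levels, and a standard error in the subgroups that differs from the primary analysis. A footnote to the forest plots should say so.

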3.4. Sample Size and Power Considerations

A total of approximately 600 subjects will be randomized in a 2:2:1:1 ratio to receive treatment with PM, PEOM, SM, or SEOM. The annual growth rate in GA lesion area is expected to have a mean of 1.47, 1.70 and 2.13 mm^2/year for PM, PEOM and Sham-Pooled (Sham) groups, respectively, as estimated from the results of a Phase 2 trial of pegcetacoplan. The standard deviation of the lesion growth is estimated to be 1.50 mm^2 based on the same Phase 2 trial data or 1.25 mm^2 based on natural history data (Holekamp N, 2019).

The power of the study for the primary endpoint is presented in Table 1 for sample size of 200 in each treatment arm. The approximation is calculated using PROC POWER ONEWAYANOVA, Statistical Analysis System (SAS) 9.4. The study power for the primary endpoint is likely larger when utilizing the longitudinal data to model the primary endpoint. The actual study power for the primary endpoint may also vary based on the distribution of the stratification factors (i.e., lesion area at screening, presence of CNV in fellow eye). Study power was not calculated for key secondary functional endpoints.

Table 1: Power to Detect a Difference among Three Groups with an Equal Size of 200 Subjects

Common Standard Deviation (mm ²)	Alpha (two-sided)	Power for a true mean of 1.47, 1.70, and 2.13 mm ² /year for PM, PEOM and Sham, respectively		
		PM vs Sham	PEOM vs Sham	Overall (Among 3 groups)
1.25	0.0495	> 99.9%	92.9%	99.9%
1.25	0.0248	99.9%	88.2%	99.7%
1.40	0.0495	99.7%	86.5%	99.3%
1.40	0.0248	99.3%	79.4%	98.6%
1.50	0.0495	99.2%	81.5%	98.4%
1.50	0.0248	98.4%	73.1%	97.0%

PM = pegcetacoplan Monthly, PEOM = pegcetacoplan Every-Other-Month; Sham = Sham Monthly + Sham Every-Other-Month

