6.3.5. Subgroup Analyses of Key Secondary Efficacy Endpoints

The subgroup analyses of the key secondary endpoints will be performed for the full 24 months. Select subgroup analyses of the key secondary endpoints may be performed at Month 12, if necessary, to support regulatory filings. The subgroups evaluated for key secondary endpoints will be the same as evaluated for the primary efficacy endpoint (see Section 6.2.5).

In addition, the following subgroup analyses will be performed:

Monocular Maximum Reading Speed

- Study eye baseline monocular maximum reading speed (<60, 60-<160, ≥160 wpm)

Mean FRI Index score

- Baseline Study Eye Status (Better-seeing Eye vs. Worse-seeing Eye)

For each endpoint, a MMRM similar to that specified for the main analysis of the key secondary endpoints (Section 6.3.2) will be used for each subgroup analysis based on the data subset for the subject subgroup of interest. Baseline covariates included in the main analysis but no longer

^[1] approximated from 6/18; see <https://icd.who.int/browse11/1-m/en#/http://id.who.int/icd/entity/1103667651>

relevant given the subgroup of interest will be excluded from the model. The estimated treatment effects (PM vs. Sham or PEOM vs. Sham) and corresponding 95% CIs and p-values from the models will be displayed graphically for each pegcetacoplan arm and each level of the subgroups specified (e.g., via forest plots).

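### SAP 6.2.5 aims to show consistency across subgroups but plans no comparison between subgroup levels

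*SAP*

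**What the plan says.** SAP 6.2.5 states the purpose: "Subgroup analyses will be performed to evaluate the consistency of the primary analysis results across subgroups defined by demographic and baseline characteristics". For the method, the approach of Section 6.2.2 "will be used for each subgroup analysis based on the data subset for the subject subgroup of interest". The effects of PM and PEOM against sham, with "corresponding 95% CIs and p-values from the models will be displayed graphically for each pegcetacoplan treatment arm and each level of the subgroups specified", are the output, for example as forest plots. Sparse levels are provided for: "as appropriate per actual subgroup sample size, levels with low sample size may be pooled to allow for an analysis to be conducted".

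The Section 6.2.2 model contains treatment, fellow-eye CNV, lesion-size category, time, time by treatment, and lesion-size category by time. The sample code in SAP Appendix 1.2.1 has the same terms. Neither has a treatment-by-subgroup term, and neither document plans one elsewhere.

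SAP 6.2.6 carries the approach to Month 24. SAP 6.3.5 carries it to the key secondary endpoints, where again "corresponding 95% CIs and p-values from the models will be displayed graphically".

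**The concern.** Consistency is a statement about the difference between levels. The planned p-values answer another question: whether the effect within one level differs from zero. A level can miss significance only because it is small, and two levels can differ in significance while their estimates are close. Without a between-level estimate, the reader must judge by eye whether the spread across levels exceeds chance.

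The list in SAP 6.2.5 is long. Without race (dropped if most subjects are of a single race) it has 17 factors: nine with two levels, five with three and three with four. That makes 9×2 + 5×3 + 3×4 = 45 levels, and two comparisons per level give 90 p-values at Month 12 before any pooling. What is at stake is how the subgroup display is interpreted, in both directions: a constant effect may look patchy, and a real difference between levels has no estimate attached to it.

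**Working it through.** **Inputs.** SAP 3.4 gives the means: "The annual growth rate in GA lesion area is expected to have a mean of 1.47, 1.70 and 2.13" mm²/year for PM, PEOM and pooled sham. The differences from sham are 2.13 − 1.47 = 0.66 and 2.13 − 1.70 = 0.43. On the SD: "The standard deviation of the lesion growth is estimated to be 1.50" mm² from Phase 2, or 1.25 mm² from natural history data. There are 200 subjects in each of the three groups. Level sizes are not in the documents; I assume equal levels, so 100 per group for a 50/50 split and 67 per group for tertiles.

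**Step 1: the plan's own power.** For a pairwise contrast in a three-group ANOVA, the noncentrality is δ / (SD × √(2/n)) with 3n − 3 degrees of freedom. At n = 200, SD 1.5 and two-sided alpha 0.0495, this gives 99.24% for PM and 81.53% for PEOM. SAP Table 1 states 99.2% and 81.5%, so the figures reproduce.

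**Step 2: power within a level, same true effect everywhere, nominal two-sided 0.05.** Example for PEOM, 50/50, SD 1.5: the SE is 1.5 × √(2/100) = 0.212, the noncentrality is 0.43/0.212 = 2.03, and with 297 df the power is 52.4%.

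**Step 3: chance of a mixed picture within one factor.** Levels share no subjects, so for L equal levels with power p each:

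P(mix) = 1 − p^L − (1 − p)^L

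For the example: 1 − 0.524² − 0.476² = 0.499.

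| Split | Arm | SD | Power per level | All levels significant | Mix |
|---|---|---|---|---|---|
| 50/50 | PEOM | 1.5 | 52.4% | 27.5% | 50% |
| 50/50 | PM | 1.5 | 87.3% | 76.2% | 22% |
| 50/50 | PEOM | 1.25 | 67.9% | 46.1% | 44% |
| 50/50 | PM | 1.25 | 96.1% | 92.3% | 7.5% |
| Tertiles | PEOM | 1.5 | 37.9% | 5.4% | 71% |
| Tertiles | PM | 1.5 | 71.7% | 36.9% | 61% |
| Tertiles | PEOM | 1.25 | 50.9% | 13.2% | 75% |
| Tertiles | PM | 1.25 | 86.0% | 63.7% | 36% |

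**Step 4: what a direct comparison does.** With a constant effect, a test of heterogeneity flags each factor about 5% of the time. A simulation of 2,000 trials over the 17 factors, with equal and independent splits, gave 5.1% to 5.3%.

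**Step 5: how sensitive it is.** For a 50/50 split, the SE of the difference between the two level effects is SD × √(2/100 + 2/100) = 0.2 × SD, or 0.30 mm² at SD 1.5 and 0.25 mm² at SD 1.25. For 80% power the true difference must be (1.960 + 0.842) × SE, or 0.84 and 0.70 mm². Both exceed the whole planned PM effect of 0.66 mm².

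**The case against.** The strongest reply is that the display is standard and harmless. Estimates and CIs stand beside the p-values, so a careful reader can compare levels, and no text makes the p-values decisive. This stands. A reader might infer that the SAP judges consistency by per-level significance, but neither document contains such a rule.

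Removing the p-values changes little by itself. With level estimates from one full-set model (597 df, tertiles, SD 1.5), the 95% CIs would exclude zero in 38.1% of cases for PEOM and 72.0% for PM, almost the same as above. This also stands: the gain lies in the added interaction estimate. That estimate is imprecise, and two arms by 17 factors still yield 34 unadjusted interaction p-values.

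Three stronger readings are tempting and not supported:

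- **Every factor will look inconsistent.** Nine of the 17 factors are binary, and for PM a 50/50 split is mixed in only 22% or 7.5% of trials. SAP 3.4 also expects longitudinal modelling to raise power, which would lower the PM figures.
- **The subset fits are unreliable because sandwich errors come from few subjects.** No calculation backs this. A tertile holds about 200 subjects over three groups, sparse levels may be pooled, and Section 6.2.2 gives simpler covariance structures if a model fails to converge.
- **Ninety p-values threaten error control.** Many factors overlap (lesion size, NL-BCVA and LLD each appear more than once), and none enters confirmatory testing. SAP 6.2.1 confines the primary hypotheses to H1a and H1b, and 6.3.1 defines the key secondary ones.

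None of this supplies the missing comparison between levels.

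**Conclusion.** The concern holds as a gap between aim and method: the SAP wants to evaluate consistency and plans no quantity that measures it. Under the plan's own effect sizes, a truly constant effect yields a mix of significant and non-significant levels within a factor in 7.5% to 50% of trials for a 50/50 split and in 36% to 75% for tertiles, depending on arm and SD. These figures assume equal level sizes, complete data, a simple comparison at Month 12 and the planned effect in every level. Unequal levels and missing data would change them, as would any variance reduction from the MMRM.

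This is a desirable improvement to a supportive analysis. It does not touch the primary estimate, the primary type I error or the criterion for a positive study.

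**What to change.** For each factor, add one MMRM on the full mITT set: the Section 6.2.2 model plus subgroup, subgroup by time, treatment by subgroup, and treatment by subgroup by time. For each active arm, report the Month 12 interaction estimate with its 95% CI and p-value beside the level estimates and CIs. Label these results exploratory and omit the per-level p-values from the forest plots. Apply the same rule to the Month 24 analyses and to the key secondary endpoints in SAP 6.3.5. State whether consistency is judged in mm² or in percent, because a constant percentage reduction gives different mm² effects where growth rates differ.

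The cost is about 17 additional models per endpoint and timepoint, built by adding terms to existing code, with no new data. The downside is low power. The SAP should say that a non-significant interaction is not proof of consistency and that the interaction CI is the main result: for a 50/50 split its half-width is about 1.96 × 0.30 = 0.59 mm² at SD 1.5, or 1.96 × 0.25 = 0.49 mm² at SD 1.25.
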